13.5.1 Open Session Report

This portion of the report provides information on study aspects such as accrual, baseline characteristics, and other general information on study status. This report is generally shared with all investigators involved with the clinical study. The reports contained in this section generally include:

- Comparison of Target Enrollment to Actual Enrollment by Month;
- Comparison of Target Enrollment to Actual Enrollment by Site;
- Overall Subject Status by Site, including: Subjects Screened, Enrolled, Active, Completed and Terminated;
- Demographic and Key Baseline Characteristics by Group;
- Treatment Duration for Subjects who Discontinue Therapy;
- Adverse Events/Serious Adverse Events by Site and Subject.

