13.4.1.1 Open Session

Members of the DSMB, the principal investigator and members of the steering committee, including the study biostatistician may attend the open session. Issues discussed will include the conduct and progress of the study, including patient recruitment, data quality, general adherence and toxicity issues, compliance with protocol, and any other logistical matters that may affect either the conduct or outcome of the study. Proposed protocol amendments will also be presented in this session. Patient-specific data and treatment group data may not be presented in the open session.

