13.4.1.2 Closed Session

The closed session will be attended only by DSMB members, and the unmasked study biostatistician. The discussion at the closed session is completely confidential. All materials from the closed session will be destroyed at the end of the meeting.

Analyses of outcome data are reviewed by masked intervention groups, including baseline characteristics, primary and secondary outcomes, adverse events, adherence and dropouts, and examination of any relevant subgroups. The DSMB may request unmasking of the data for either safety or efficacy concerns. Procedures to accomplish unmasking of either individual or treatment group data are to be specified in the Data and Safety Monitoring Plan.

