13.5.2 Closed Session Report

This report may contain data on study outcomes, including safety data. Data will be presented by masked treatment groups; however, the DSMB may request that the treatment groups be unmasked to ensure that there are no untoward treatment effects. The Closed Session Report is considered confidential and should be destroyed at the conclusion of the meeting. Data files to be used for interim analyses should have undergone established editing procedures to the extent possible. This report should not be viewed by any members of the clinical study except the designated unmasked study statistician.

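### The open DSMB report lists by-group baseline tables and subject-level adverse events that the charter bars from the open session; the by-group table puts the blind at risk

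*Combined protocol and SAP*

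**What the plan says.** Section 13.4.1.1 (Open Session) sets the rule: "Patient-specific data and treatment group data may not be presented in the open session". It also names the audience: "Members of the DSMB, the principal investigator and members of the steering committee, including the study biostatistician may attend the open session".

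Section 13.5.1 (Open Session Report) lists what the matching report generally contains. Two of the items are "Demographic and Key Baseline Characteristics by Group" and "Adverse Events/Serious Adverse Events by Site and Subject". On circulation it says: "This report is generally shared with all investigators involved with the clinical study".

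The closed side is more tightly drawn. Section 13.4.1.2 (Closed Session) says: "Analyses of outcome data are reviewed by masked intervention groups, including baseline characteristics, primary and secondary outcomes, adverse events". Section 13.5.2 (Closed Session Report) says: "Data will be presented by masked treatment groups", and restricts access: "This report should not be viewed by any members of the clinical study except the designated unmasked study statistician".

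Section 9.4 promises a double blind with separate blinded and unblinded teams. Section 13.5 has the unmasked biostatistician prepare the reports, quarterly or semi-annually.

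**The concern.** A by-group baseline table is treatment-group data, and an adverse-event listing by subject is patient-specific data. Section 13.4.1.1 bars both from the open session; 13.5.1 lists both for that session's report. If 13.5.1 is followed as written, an unmasked source sends by-group tables to investigators who are meant to be blinded. The report with the wider audience also has the weaker protection, because only the closed report must use masked groups.

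What is at stake is allocation masking. Efficacy rests on the IIEF, which section 8.2.7 describes as a self-evaluation scale and which can respond to expectation. The primary endpoint needs judgement too: section 12.2 leaves seriousness to the investigator's view, and section 12.3 requires a reasonable possibility of causation. An investigator who knew or suspected a man's group could be influenced in making that attribution.

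**Working it through.** No figure in the plan underlies this point, so there is none to reproduce. The check compares the sections and then asks how much a by-group table could give away.

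**1. The sections side by side**

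| | Open session, 13.4.1.1 | Open report, 13.5.1 | Closed side, 13.4.1.2 and 13.5.2 |
|---|---|---|---|
| Data by treatment group | Barred | Baseline listed by group | Baseline and adverse events by group |
| Patient-level data | Barred | Adverse events listed by subject | Not named |
| Masked labels required | Does not arise | Not stated | Yes |
| Audience | DSMB, principal investigator, steering committee, biostatistician | Generally all investigators | DSMB and unmasked statistician |

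The conflict is present for both items.

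**2. What two successive tables disclose**

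Suppose a group has n1 men with mean M1 at one report, and n2 men with mean M2 at the next. The total for its new members is n2·M2 − n1·M1. With means rounded to one decimal, that total is known to within ±0.05·(n1 + n2). An investigator who knows the new men's own values can test each possible split against it. If the new men divide evenly between groups:

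- 20 enrolled, 4 new: 6 possible splits; band ±0.05·(10 + 12) = ±1.1.
- 40 enrolled, 8 new: 70 possible splits; band ±0.05·(20 + 24) = ±2.2.
- 20 enrolled, 12 new: 924 possible splits; band ±0.05·(10 + 16) = ±1.3.

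Few new men means few splits to separate. With one new man, the change in group size alone gives his group.

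**3. How often the split is fully determined**

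A simulation used 400 runs per setting. Its inputs are assumptions: each report gives n, mean age and mean IIEF-EF per group to one decimal; the investigator knows each new man's age and IIEF-EF; ages are normal with mean 56 and SD 11, limited to 30-80; IIEF-EF is uniform on 12-25; and allocation is balanced over all men enrolled at the later report.

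| New men since last report | Already enrolled | Split fully determined |
|---|---|---|
| 4 | 0 / 20 / 40 | 99% / 99% / 96% |
| 8 | 0 / 20 / 40 | 93% / 85% / 57% |
| 12 | 20 | 29% |

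Accrual is not stated. If, as an assumption, 60 men enrol over one to two years, quarterly reports would cover 60/8 = 7.5 to 60/4 = 15 new men each, and semi-annual reports 60/4 = 15 to 60/2 = 30.

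**4. From group to treatment**

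Sorting men into groups is not the same as knowing their treatment. The second step follows if labels are open, if the report uses the protocol's own letters (the synopsis and section 8 define Group A as active and Group B as placebo/sham), or if a masked label is linked by another route, such as an unblinding under 9.4 of a man whose label has been inferred. In the last case, only men whose labels have been inferred are exposed.

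**5. The adverse-event listing**

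The item is by site and subject, not by group. At the rates in section 12.1, 30 active men would have 30 × 0.1% = 0.03 to 30 × 1.1% = 0.33 expected cases of each shockwave-related event type, and 30 × 5% = 1.5 of each PRP pain item. Section 9.2.1 gives controls a similar injection followed by the same compression, so local events are plausible in both arms. Such sparse, shared events would rarely identify an arm.

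**The case against.** The strongest reply is that 13.5.1 is untailored template text. It says what such reports generally contain and with whom they are generally shared, and it asks for figures by site although section 5.1 says there are no additional sites. A statistician could satisfy both sections by leaving the barred items out. This stands in part: a reader might infer that the two sections can never both be obeyed, or that investigators will certainly receive these tables, and the text shows neither. It does not remove the conflict, because anyone following the 13.5.1 list as written breaches 13.4.1.1. Separating session from report does not help either, since the document is named for the open session and circulates more widely.

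A second reply is that investigators already have the adverse-event data, because events are reviewed at every treatment and follow-up visit and grade 3-5 events go to research committee meetings (12.1.2). This stands. The listing breaches the charter's own rule but adds little risk to the blind.

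A third reply is that reconstruction takes deliberate effort and favourable accrual, that participants do not receive the report, and that the technician giving therapy does not assess outcomes (9.4). This also stands, and it limits the size of the risk without removing it.

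**Conclusion.** The inconsistency is real and should be corrected. Its substance is the by-group baseline table, which would go to blinded investigators with no masking requirement in a 60-man trial. How often it would sort men into groups ranges from nearly always to under a third of the time across the settings examined. That range rests on assumed table contents, precision and accrual, and on an investigator who knows each new man's values.

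Three stronger readings are not supported. A reader might infer that one emergency unblinding would expose every participant; it would expose only men whose labels had already been inferred. A reader might infer that the subject-level listing unblinds; it carries no group code and repeats what investigators recorded. A reader might infer that interim efficacy leaks; baseline tables carry no outcome data. Nor do the documents show that any blind has been or will be broken.

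**What to change.** In 13.5.1, change the baseline item to characteristics pooled over groups, and the adverse-event item to pooled counts by type and grade. Add the by-group baseline tables, with masked labels, and the subject-level adverse-event and serious adverse-event listings to the closed report in 13.5.2. Sections 13.4.1.1, 13.4.1.2, 13.5.1 and 13.5.2 then agree.

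The cost is a charter edit, which section 13.1 already allows with the DSMB's agreement, and a different split of tables that the unmasked biostatistician already prepares. The DSMB loses no information, and no analysis or sample size changes.

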13.5.2 Closed Session Report

This report may contain data on study outcomes, including safety data. Data will be presented by masked treatment groups; however, the DSMB may request that the treatment groups be unmasked to ensure that there are no untoward treatment effects. The Closed Session Report is considered confidential and should be destroyed at the conclusion of the meeting. Data files to be used for interim analyses should have undergone established editing procedures to the extent possible. This report should not be viewed by any members of the clinical study except the designated unmasked study statistician.

13.6 Documentation of DSMB Meetings

13.6.1 Meeting Summary

A formal summary containing the DSMB's input on the conduct of the study and their recommendation regarding continuation of the study will be prepared by the DSMB Executive Secretary. Each DSMB summary will include the DSMB's recommendation regarding continuation or termination of the study. The DSMB meeting summary will not include unmasked data, discussion of the unmasked data, or any other confidential data. Once completed, the summary is sent to the DSMB members for their review and concurrence. When the summary is satisfactory to the DSMB members and concurrence with the summary is received, the summary will be sent to the PI. It is the responsibility of the PI to distribute the summary to all co-investigators.

It is the responsibility of the study investigators to assure that the DSMB summary is submitted to all the Institutional Review Boards (IRBs) associated with the study.

13.7 Confidentiality and Objectivity

All materials, discussions and proceedings of the DSMB are completely confidential. Members and other participants in DSMB meetings are expected to maintain confidentiality. Closed session meeting materials should be destroyed in a secure manner (shredding) following each meeting.

In order to maintain their objectivity, DSMB members are expected not to discuss the study/studies with the investigators except during DSMB meetings.

14. Statistical Considerations

14.1 Data Analysis Plan

Analysis plan: Continuous data will be analyzed using ANOVA with repeated measures, or student's T-Test (where applicable) in order to compare differences between the treatment and control groups. For categorical data, Fisher's Exact test to determine differences between groups. Statistical significance will be evaluated using $\alpha=0.05$.

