2.4 Combination Restorative Therapy for Erectile Dysfunction

The development of ED therapeutics that focus on neurovascular regeneration and repair strategies are of great importance. A large body of *pre-clinical* work has demonstrated the effect of SWT alone (monotherapy) on angiogenesis and progenitor / stem cell recruitment for ED [2, 3, 8-11]. PRP monotherapy importantly is also supported by well-defined mechanistic insights obtained from rigorously conducted animal studies [12-19]. All the previous studies in humans have evaluated either IIEF scores and / or penile Doppler ultrasound hemodynamic parameters, but there has not been evaluation of the treatment as a combination. The proposed mechanisms of both interventions would

suggest that the combination therapy would act in a synergistic manner, with superiority over monotherapy. Success of our proposed work could fundamentally change the standard of care for ED and substantially improve the quality of life for tens of millions of men.

3. Study Objectives

3.1 Primary Objective:

To investigate and compare the safety of PRP and SWT vs placebo/sham treatment in men with mild-moderate ED.

3.2 Secondary Objective:

To study the treatment efficacy of PRP and SWT treatment vs placebo/sham treatment in men with mild-moderate ED.

4. Study Endpoints

4.1 Primary Endpoint (safety):

- Incidence of treatment emergent serious adverse events (TE-SAEs) in all patients during the study period. Adverse events will be recorded at every visit. The following contains a list of the anticipated adverse events:
 - Pain
 - Bruising
 - Swelling
 - Edema
 - Allergy
 - Penile Fracture
 - New Penile Curvature

4.2 Secondary Endpoints (efficacy):

- Change in IIEF-EF score from baseline to 3 and 6 months post-therapy compared to control group.
- Percentage of subjects that achieve minimal clinically important difference (MCID) in IIEF-EF from baseline to 3 and 6 months post-therapy compared to control group,
- Percentage of subjects who either decrease or discontinue use of PDE5i after three months post-therapy compared to control group.

4.3 Exploratory Endpoints:

- Differences in Doppler ultrasound parameters (PSV and EDV) from baseline to 6 months post-therapy compared to control group.
- Treatment satisfaction as assessed by EDITS questionnaire in all subjects.
- Changes in IPSS questionnaire between treatment and control group.
- Perceptions of therapeutic allocation between treatment and control group.

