5.1 Additional Study Sites

No additional study sites.

6. Study Population

60 males with ED of organic origin. All patients will be regular PDE5i users/responders. Men with ED will be evaluated by IIEF-EF domain and eligible patients will be randomized to one of 2 treatment groups with an equal allocation ratio (1:1). Participants who do not meet eligibility criteria will be considered a screen failure and will not receive the study therapy.

6.1 Inclusion criteria:

In order to participate in this study, a patient must:

- 1) Be Male
- 2) Be 30 to 80 years of age (inclusive).
- 3) Be able to provide written informed consent.
- 4) Have a diagnosis of mild to moderate ED (12-21) or mild ED (22-25) based on IIEF-EF questionnaire score.
- 5) Be in a stable heterosexual relationship, and have a minimum of 2 sexual attempts per month for at least one month prior to enrollment..
- 6) Agree to comply with all study related tests/procedures.

6.2 Exclusion criteria:

In order to participate in this study, a patient must not have any of the following:

- 1) Previous penile surgery of any kind (except circumcision and condyloma removal), such as penile lengthening, penile cancer surgery, penile plication, grafting.
- 2) Previous history of priapism, penile fracture, Peyronie's Disease, or penile curvature that negatively influences sexual activity,
- 3) Abnormal morning serum testosterone level defined as a value lower than 300 ng/dL ($\pm 5\%$).
- 4) Psychogenic ED as determined by study investigator.
- 5) Patients using ICI for management of ED
- 6) Patients with generalized polyneuropathy, neurological conditions, or psychiatric disease (such as bipolar disorder or depression).

- 7) Have a serious comorbid illness or condition that, in the opinion of the investigator, may compromise the safety or compliance of the subject or preclude successful completion of the study.
- 8) History of consistent treatment failure with PDE5 inhibitors for therapy of ED.
- 9) Poorly controlled diabetes as indicated by Hemoglobin a1c > 9%.
- 10) Use of antiplatelet medication

7. Identification and Enrollment of Subjects

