8.2 Description of Study Procedures

- 8.2.1 *Informed Consent:*** Refer to Section 7.3 for details regarding the informed consent process. Study procedures will be completed only after participants have signed the informed consent documentation.
- 8.2.2 *Demographics:*** Demographic characteristics will be recorded including: date of birth, gender, marital status, race and ethnicity.
- 8.2.3 *Medical History:*** Assessment of current and past medical, surgical, and social history will be conducted.
- 8.2.4 *Physical Examination:*** Genitourinary/Reproductive system physical exam will be performed.
- 8.2.5 *Phone Call:*** Participants will be contacted by telephone to assess safety outcomes during long term follow up.
- 8.2.6 *Doppler Ultrasound:*** Penile Doppler ultrasound will be performed as standard of care for the management of erectile dysfunction. Results from within the past 12 months can be extracted from the medical record for use in this study.
- 8.2.7 *International Index of Erectile Function (IIEF) Questionnaire:*** This validated 15-item self-evaluation scale provides pre and post treatment clinic evaluations of erectile function, orgasmic function, sexual desire, satisfaction in sexual intercourse and general satisfaction. If the subject has completed the IIEF questionnaire within the past 6 months, those results may be requested and used for the purpose of this research study. Questionnaires will be completed prior to therapy at injection visits.
- 8.2.8 *Erectile Dysfunction Inventory of Treatment Satisfaction (EDITS) Questionnaire:*** This is a psychometrically sound questionnaire used to assess satisfaction with medical treatment modalities for erectile dysfunction.
- 8.2.9 *Visual Analogue Pain Scale (VAS):*** The visual analog scale (VAS) is a validated, subjective measure for acute and chronic pain. Scores are recorded by making a handwritten mark on a line that represents a continuum between “no pain” and “worst pain”.
- 8.2.10 *International Prostate Symptom Score (IPSS):*** This eight-question screening tool used to track symptoms of benign prostatic hyperplasia (BPH)
- 8.2.11 *Subject Global Assessment (SGA):*** In this single-question survey, subjects will be asked which treatment arm they believe that they had received (placebo/sham or active therapy).
- 8.2.12 *Randomization:*** Refer to Section 9.3 for details about randomization plan

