8.3.3 Follow Up Visits: Months 3 and 6 Post-Treatment

Follow up visits will occur within 90 ± 14 days (Month 3) and 180 ± 14 days (Month 6) days after final treatment visit. Refer to table 1 for procedures to be performed at the follow up visits visit.

9. Investigational Product

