14.2 Sample Size

Inclusion Criteria are men with IIEF scores >11 which includes men with mild (IIEF 16-21) and mild/moderate (12-16) Erectile dysfunction. Minimal clinically important difference (MCID) for these groups are an increase of 2 for mild and 5 for moderate ED. Previous studies on the effect of placebo show about a 15% improvement in men with mild to moderate ED. Therefore, 15% of the placebo group is expected to meet MCID. Results from the PRP safety study by Matz et al. 2018, which showed a mean improvement in IIEF of 4.14 points in seven patients with ED after PRP. In the interventional group, we expect 50% to meet MCID. At 80% power, we will therefore need 30 patients in each group to detect a difference of 35% between treatment and placebo arms.

$$\text{Sample size} = \frac{2(Z_{\alpha/2} + Z_{\beta})^2 P(1-P)}{(P_1 - P_2)^2}$$

$$24 = (2*(1.96+0.84)^2 * (0.25*(1-0.25))) / (0.35^2)$$

Assuming attrition of approximately 20%, an additional 6 participant slots will be added to each group for a total sample size of 60 subjects.

15. Risks and Benefits

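### IIEF-EF change is to be tested without baseline as a covariate, and Section 14.1 does not say which test or term decides

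*Combined protocol and SAP*

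**What the plan says.** Section 14.1 (Data Analysis Plan) is the whole statistical method. For continuous outcomes it says "Continuous data will be analyzed using ANOVA with repeated measures", with Student's t-test as an alternative where it applies. It adds Fisher's exact test for categorical outcomes and an alpha of 0.05. It names no covariate, no term to be tested, no analysis population and no statistical method for missing data. Section 10.1 asks only that the reason for missing data be recorded.

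The endpoint concerned is the first secondary efficacy endpoint in Section 4.2: "Change in IIEF-EF score from baseline to 3 and 6 months post-therapy compared to control group". The primary endpoint in Section 4.1 is the incidence of treatment-emergent serious adverse events.

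The schedule in Section 8.1 has the IIEF at screening, Month 3 and Month 6. Section 6.1 requires an IIEF-EF score of 12 to 25 at entry, so a baseline value should exist for every randomised man. Section 14.2 plans for dropout: "Assuming attrition of approximately 20" per cent.

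**The concern.** Subtracting baseline is not the same as adjusting for it. A change score fixes the weight on baseline at 1, whereas ANCOVA estimates that weight from the data. In large samples ANCOVA is therefore at least as precise as the change score. With about 24 evaluable men per arm, precision that costs no extra men or visits is worth having.

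The second problem is that the test is left open. Section 14.1 offers two methods joined by an or. With three IIEF time points, repeated-measures ANOVA could mean several models: two or three levels of time, and a test of the group effect or of the group-by-time interaction. These can give different answers on the same data. Unless one is named in advance, the choice can be made after the results are seen. This part of the point does not depend on any assumed SD or correlation.

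**Working it through.** **1. The plan's own figure.** Section 14.2 sizes the trial on the proportion reaching MCID, not on mean IIEF-EF. It expects that "15% of the placebo group is expected to meet MCID", against 50% on active treatment. Its formula with its printed P = 0.25 gives 2 × (1.96 + 0.84)² × 0.25 × 0.75 / 0.35² = 24.0 per arm, and 24 / 0.8 = 30 per arm. This reproduces. I use 24 evaluable men per arm below.

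**2. Inputs the documents do not give.** No SD and no baseline to follow-up correlation r is stated. I assume a follow-up SD (s_y) of 5.5 and r = 0.3, 0.5 and 0.7, with two values for the baseline SD (s_x):
- s_x = 5.5, equal to follow-up.
- s_x = 4.03, for whole-number scores spread evenly over 12-25: √((14² − 1)/12) = √16.25.

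**3. Formulas.** The variance of the arm difference at one visit is proportional to:
- change score: s_y² + s_x² − 2·r·s_x·s_y
- ANCOVA: s_y²(1 − r²)

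The first minus the second equals (s_x − r·s_y)². The gain is never negative in large samples, and it vanishes at r = s_x/s_y. With s_x = 4.03 that is r = 4.03/5.5 = 0.73. With equal SDs the ratio of ANCOVA to change score simplifies to (1 + r)/2.

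**4. Results.** ANCOVA variance is 30.25 × (1 − r²). Change-score variance is 60.50 − 60.50·r for equal SDs, and 46.50 − 44.34·r for s_x = 4.03.

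| r | ANCOVA | Change, s_x = 5.5 | Reduction | Change, s_x = 4.03 | Reduction |
|---|---|---|---|---|---|
| 0.3 | 27.53 | 42.35 | 35% | 33.20 | 17% |
| 0.5 | 22.69 | 30.25 | 25% | 24.33 | 7% |
| 0.7 | 15.43 | 18.15 | 15% | 15.46 | 0% |

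**5. Cost of the covariate.** With 48 men, one covariate inflates the ANCOVA variance by about 1 + 1/44 = 1.023. For s_x = 4.03 the net variance ratios are 0.829 × 1.023 = 0.85, 0.933 × 1.023 = 0.95 and 0.998 × 1.023 = 1.02. The last is a small loss.

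**6. In terms of power.** For an assumed true effect of 4 points, 24 men per arm and two-sided 0.05 (noncentral t, ANCOVA with the cost in step 5):

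| r | Change, s_x = 5.5 | Change, s_x = 4.03 | ANCOVA |
|---|---|---|---|
| 0.3 | 55% | 65% | 72% |
| 0.5 | 69% | 79% | 80% |
| 0.7 | 89% | 93% | 93% |

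**7. Which repeated-measures test.** Suppose baseline is one of three levels and the group main effect is tested. The expected difference is then (0 + d + d)/3 = two-thirds of d. With all SDs 5.5, r = 0.5 and a correlation of 0.7 between Months 3 and 6, power for that test is about 50%. The mean of the two change scores has about 76% under the same assumptions, and the univariate group-by-time test about 75%. The label in Section 14.1 covers all three.

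**8. Missed visits.** If 20% miss Month 6 and, by assumption, a further independent 10% miss Month 3, an analysis needing complete rows keeps 60 × 0.8 × 0.9 = 43 men. An analysis of Month 6 alone keeps 60 × 0.8 = 48. In simulations with equal SDs and data missing at random, a joint model of both visits cut the Month 6 variance by only about 0-4% beyond ANCOVA on the available men. Most of the benefit comes from the covariate.

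**The case against.** The strongest objection concerns size. The reductions of 35%, 25% and 15% need equal SDs at baseline and follow-up, and the entry range makes that doubtful: a baseline SD of 5.5 within 12-25 would require most men to sit near the two ends. This stands. With a baseline SD near 4, power at r = 0.5 moves only from about 79% to 80%. Section 8.2.7 also allows an older form as baseline: "If the subject has completed the IIEF questionnaire within the past 6 months, those results may be requested and used". That could lower r, which would enlarge the gain over a change score, but the documents do not allow it to be measured.

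Two stronger readings are tempting, and the documents support neither.
- A reader might infer that the planned ANOVA has only about half the power it should. That follows only if baseline is a level and the group main effect is tested. Section 14.1 does not specify this, and an endpoint defined as change points more naturally to change scores or the interaction.
- A reader might infer that the plan drops men with a missed visit. No such rule is written. Dropping them is the default of classical repeated-measures ANOVA; a per-visit t-test loses only men missing that visit.

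It is also fair to say that a mixed model is not essential. ANCOVA per visit captures most of the gain. A mixed model keeps men with one follow-up score but not men with none, and it assumes data missing at random.

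**Conclusion.** The point holds in a limited form. Section 14.1 does not use baseline IIEF-EF as a covariate and does not say which test or term decides. Both can be put right without extra men, visits or data.

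The expected gain over a change-score t-test runs from 35% of variance (r = 0.3, equal SDs) down to nothing (r = 0.7, baseline SD about 4), before a cost of about 2%. All of this rests on assumed SDs and correlations. The dilution to two-thirds and the loss of men with a missed visit are conditional on how the ANOVA is run, and are not properties of the plan as written.

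The reason for change that rests on no assumption is the open choice of test. The endpoint is secondary, so this is a recommended improvement rather than a defect that threatens the trial. The primary safety endpoint and the sample size of 60 stay as they are.

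**What to change.** Before unblinding, replace the sentence on continuous data in Section 14.1 with one named analysis of IIEF-EF at Months 3 and 6. Either of these would do:
- ANCOVA at each visit, with arm and baseline IIEF-EF.
- A mixed model for repeated measures with arm, visit, arm-by-visit, baseline and baseline-by-visit.

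Include every randomised man with at least one post-baseline score, in his assigned arm. Under per-visit ANCOVA he contributes at the visits he attended. Report the adjusted difference with 95% CI at each visit. State the missing-at-random assumption if the mixed model is chosen. Use ANCOVA with the baseline value for PSV, EDV and IPSS, which are scheduled once after baseline.

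The cost is SAP wording, standard software and about one degree of freedom per visit.
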